1. Test the effectiveness of PfR in modifying key outcomes on parent-child relationships and relationships between partners which underlie violence against children and girls/women. The trial will be powered to detect meaningful change in four primary outcomes: parent-reported and child-reported harsh parenting and partner conflict. Secondary outcomes include positive parenting, parental support for children's education, child behaviour problems, parent/child mental health problems, material provision for children (all parent- and child-report), as well as inequitable gendered socialisation and parenting self-efficacy, including protecting children from sexual abuse (parent-report only).
2. Examine the cost effectiveness of PfR using incremental cost-effectiveness analyses (CEA) based both on the primary outcomes of harsh parenting and partner conflict as well as on disability-adjusted life years (DALYs);
3. Examine how three implementation variables – rural vs peri-urban locality, previously established groups vs new groups, and professional vs non-professional facilitators – affect participation, programme fidelity, and quality of delivery (measured quantitatively);
4. Examine the impact of implementation variables – participant engagement and quality of delivery by facilitators – on primary outcomes of parent- and child-report of harsh parenting and partner conflict. We will also examine associations between baseline characteristics and participant engagement to further understand potential barriers to participation and whether there are particularly vulnerable families that have greater challenges in attending the programme.
5. Qualitatively investigate five elements of implementation: (i) what training facilitators need (length, follow-up, who delivers training, location, etc.); (ii) what supervision facilitators need (frequency, by whom, nature of feedback, etc.); (iii) targeting of PfR at the most vulnerable families and how this can be done; (iv) disseminating PfR's messages beyond those participating in group sessions to operate at a community, as well as individual, level; (v) differences between Wakiso and Amuru Districts in facilitative and hindering contextual factors. We will explore how these affect participation, programme fidelity, quality of delivery, participant response and community-wide impact.

Hypotheses

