Hypothesis 1: PfR will significantly reduce rates of child maltreatment at 3-months follow-up, as measured by parent and child-reports of the ICAST-Trial Scale, in comparison to a control group receiving a one-hour lecture on parenting and partner relationships.

Hypothesis 2: PfR will significantly reduce rates of partner conflict at 3-months follow-up, as measured by parent and child-reports of an adapted version of the Conflict Tactics Scale and WHO Coercion scale, in comparison to a control group receiving a one-hour lecture on parenting and partner relationships.

Hypothesis 3: PfR will have a significant effect on secondary outcomes associated to the risk violence against children and intimate partner violence at 3-months follow-up, including positive parenting,

parental support for children's education, child behaviour problems, parent/child mental health problems, and material provision for children (all parent- and child-report), as well as inequitable gendered socialisation and parenting self-efficacy, including protecting children from sexual abuse (parent-report), in comparison to a control group receiving a one-hour lecture on parenting and partner relationships.

Hypothesis 4: PfR will be cost-effective in terms of incremental cost-effectiveness analyses (CEA) based both on the primary outcomes of harsh parenting and partner conflict as well as on disability-adjusted life years (DALYs).

Hypothesis 5: We hypothesise that the following modalities of PfR delivery on implementation outcomes and cost (i.e., attendance, competent adherence, and cost-effectiveness):

A) Geographical location (urban vs peri-urban). We hypothesise that there will be no difference between urban and peri-urban delivery on implementation and cost outcomes. While families living in higher density areas may have more accessibility to other support services, rural families may be easier to recruit due to closer inter-family dynamics.

B) Group composition (existing vs new). We hypothesise that recruitment from existing community groups (e.g., microfinance savings groups) will have higher levels of implementation and more cost-effective than newly formed groups. Higher participation rates will, in turn, result in reductions VAWC (via indirect effects).

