C) Facilitator Experience (professional vs community). We hypothesise that although professional facilitators may achieve higher levels of implementation, community facilitators may be a more cost-effective approach and may also result in better implementation due to stronger buy-in at the community level. As a result, there will be no difference between components on VAWC (via indirect effects).

8. Trial design

We will use an effectiveness-implementation hybrid type 2 design to a) determine the effectiveness and cost-effectiveness of PfR, and b) determine the feasibility and impact of three different implementation strategies in terms of programme delivery.[21] We will conduct a cluster randomised controlled trial (cRCT) in a total of 54 clusters (1:1 intervention: control; 4 groups of 10 parents per cluster, 50% male 50% female, 2,160 in total or 1,080 adult participants per arm). In addition, approximately 1,080 children 10-14 years will be assessed ($N = 540$ per arm). We will also assess the quality of delivery of PfR in terms of competent adherence of 108 facilitators (1 per group, 4 per cluster).

We will also examine three different factors related to programme implementation within the clusters allocated to PfR (approximately 27 clusters, 40 parents per cluster): 1) geographical location (rural vs. peri-urban), 2) group composition (existing vs. newly formed groups), and 3) facilitator experience (experience vs. novice). Efforts will be made to have equal numbers of clusters receiving each type of component by testing every combination of implementation components in eight different experimental conditions ($N 3$ clusters and 120 families per condition).

Section 3: Methods

9. Study setting

The study will be conducted in two districts, Wakiso and Amuru, each of them contributing parental participants to both intervention and control arms. Participating clusters will either be villages or wards (i.e., groups of villages) depending on their population size and geographical proximity.

10. Eligibility criteria

Participants must have provided written, informed consent prior to the occurrence of any study procedures.

Inclusion criteria for participating parents or caregivers:

1. Age 18 or older;
2. Primary caregiver responsible for the care of a child between the ages of 10 and 14;
3. Agreement to participate in the PfR programme if allocated to the treatment condition;
4. Provision of consent to participate in the full study.

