For the evaluation of implementation components, we conducted similar sensitivity power analyses in order to calculate the minimum detectable Cohen's D effect size to obtain a significant effect of each component level on implementation outcomes of participation rates and implementation quality. Following recommendations for component selection by Collins et al. (2016) and Watkins et al. (2016), we assumed a Type 1 error of $p < 0.10$, and 80% power with a sample size of 480 adults and an ICC of

0.05. Thus, this sample size has sufficient power to detect significant component effects at Cohen's $d = .26$ on implementation outcomes (i.e., implementation fidelity, competent adherence, and participation).

14. Interventions

Intervention group – Parenting for Respectability

PfR was developed over five years following the Six Steps for Quality Intervention Development (6SQuID) model [22]. It initially underwent formative evaluation over two years (2014-2016) with six groups in three villages in Wakiso District [20]. *PfR* is a 16-session manualised programme starting with nine single sex sessions followed by seven mixed sex sessions, delivered once a week by two local facilitators who receive one week's training [23]. The programme draws on parents' pre-existing motivation to maintain respectability, largely achieved through children's good behaviour and respect for elders and builds on parents' existing skills and experience. Activities were developed specifically for PfR or adapted from other parenting programs, including *Project H*, *Stepping Stones*, *Mema kwa Jamii*, the *International Child Development Programme* and *Parenting for Lifelong Health* [24]. The programme addresses four familial processes associated with GBV and VAC: poor parental bonding and child attachment; harsh parenting; inequitable socialisation by gender and parental conflict. A particular goal is to involve fathers, whom most parenting programmes find hard to recruit, and the first nine sessions are delivered in single-sex groups. The intervention's rationale, program theory and formative evaluation are described elsewhere [25].

Control group - Lecture

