Time cost for delivery – Facilitator Report

Time cost for delivery will be collected from facilitator weekly reports and based on the time spent on training, preparation, travel to and from, and delivery of each session/lecture. The total time will be summed for each facilitator and then mean scores will be created for the sample.

[Time Frame: 8-months post-baseline]

Implementation fidelity – Facilitator Report

Implementation fidelity by programme facilitators of the PfR programme will be examined using self-report checklists by the programme facilitators. They will report on 5 items per session/lecture ranging from an impression of the quality of delivery to the proportion of the session activities they were able to deliver (0 = No time for it to 5 = all of the activities).

[Time Frame: 8-months post-baseline]

Competent adherence – Observational

Competent adherence will be assessed using the PfR Facilitator Assessment Tool (PfR-FAT) [39]. The PfR-FAT was developed by the study investigators and programme developers to assess the proficiency of programme delivery by facilitators as a prerequisite to certification. Three standard behaviour categories are based on the core process skills (25 items), includes modelling skills (6 items, e.g., “give positive, specific, and realistic instructions”), collaborative facilitation (7 items, e.g., “accept participant responses verbally by reflecting back what the participant says”), and group management and leadership

skills (12 items, e.g., “use open-ended questions during group discussions”). Items are summed to create a total score of competent adherence.

[Time Frame: 8-months post-baseline]

Qualitative outcomes

Qualitative data will be collected using live observation of programme delivery (at least 1 observation per group, N=32); in-depth interviews with senior implementation staff (N=4), trainers of facilitators (N=2) and a sample of facilitators (N=16); focus group discussions with caregivers (N=8, 10 per FGD). In addition, data will be collected through semi-structured interviews with Wakiso and A District Community Development Services (N=4) who will provide supervision of the NGO implementing partner (SOS) and from a sample of local community leaders (N=8), each lasting from 60 – 90 minutes.

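### Section 13 applies a detectable effect derived from adults (d = 0.26) to competent adherence, which is scored on 108 facilitators and has a detectable effect of about 0.5

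*Protocol*

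**What the plan says.** - **Section 13, Power calculations.** The component calculation takes a type I error of 0.10 and "80% power with a sample size of 480 adults and an ICC of" 0.05. The resulting Cohen's d of 0.26 is claimed "on implementation outcomes (i.e., implementation fidelity, competent adherence, and participation"). No other detectable effect is given for these outcomes.
- **Section 8, Trial design.** The study will assess "competent adherence of 108 facilitators (1 per group, 4 per cluster"). The PfR arm has about 27 clusters of 40 parents, so 27 × 4 = 108 groups and about 1,080 adults.
- **Section 15, Process outcomes.** The competent adherence tool was built "to assess the proficiency of programme delivery by facilitators as a prerequisite to certification". On scoring: "Items are summed to create a total score of competent adherence". Fidelity is a facilitator self-report, completed per session. Participation is measured on attending parents and families.
- **Section 7.** Objective 3 asks how the three components "affect participation, programme fidelity, and quality of delivery (measured quantitatively"). Hypothesis 5 concerns "implementation outcomes and cost (i.e., attendance, competent adherence, and cost-effectiveness"), and part A predicts "no difference between urban and peri-urban delivery on implementation and cost outcomes".

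**The concern.** A detectable effect belongs to a unit of observation. Adults attend sessions, so an adult count can support a statement about participation. Adults do not carry a competent adherence score; facilitators do, and there are far fewer of them. One figure covers both kinds of outcome, and the protocol gives no facilitator-level figure beside it.

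What is at stake is how the component results are read. Section 13 tells the reader that a true difference of 0.26 in competent adherence would be missed 2 times in 10. If the real miss rate is about 6 in 10, the study's ability to compare quality of delivery across location, group type and facilitator type is overstated for an outcome that Hypothesis 5 names.

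**Working it through.** **Inputs**
- Type I error 0.10, power 80%, ICC 0.05, 480 adults, d = 0.26: Section 13.
- Two-sided test: assumed, because Section 13 calls this calculation similar to its two-tailed main one.
- Equal numbers per component level: Section 20 places each component in half of the conditions.
- 108 facilitators, 4 per cluster; 27 clusters of 40 parents: Section 8.
- 24 clusters and 960 adults per arm after cluster loss: Section 13.
- Facilitator-level ICC: not given, so a range is shown.
- One score per facilitator: assumed.

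**Formula.** With N units in all and m per cluster, the design effect is DE = 1 + (m − 1) × ICC, and

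detectable d = (1.645 + 0.842) × 2 / √(N / DE).

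Solving for d = 0.26 gives an effective N of (2.487 × 2 / 0.26)² ≈ 366.

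**Step 1: the plan's own figure.** What the 480 adults count is not stated, and the result depends on it (ICC 0.05):

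| Reading | DE | Effective N | Detectable d | Power at 0.26 |
|---|---|---|---|---|
| 480 in total, 10 per group | 1.45 | 331 | 0.27 | 76% |
| 480 in total, 40 per cluster | 2.95 | 163 | 0.39 | 51% |
| 480 per level: 960 in 24 clusters of 40 | 2.95 | 325 | 0.28 | 76% |
| 1,080 in 27 clusters of 40 | 2.95 | 366 | 0.26 | 80% |

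So 0.26 matches the full PfR arm of Section 8. It does not follow from 480 adults with the protocol's own group or cluster sizes.

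**Step 2: competent adherence, 108 facilitators, m = 4**

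| ICC | DE | Effective N | Detectable d | Power at 0.26 |
|---|---|---|---|---|
| 0 | 1.00 | 108 | 0.48 | 38% |
| 0.05 | 1.15 | 93.9 | 0.51 | 35% |
| 0.10 | 1.30 | 83.1 | 0.55 | 32% |
| 0.20 | 1.60 | 67.5 | 0.61 | 28% |
| 0.30 | 1.90 | 56.8 | 0.66 | 25% |

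At ICC 0 the power is Φ(0.26 × √108 / 2 − 1.645) = Φ(−0.294) = 38.4%. Counting the opposite tail as well makes it 38.6%, hence 35 to 39% for ICC 0 to 0.05.

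**Step 3: sensitivity**
- 96 facilitators (24 clusters): d = 0.51 to 0.54 and power 32 to 36%, for ICC 0 to 0.05.
- 108 facilitators, noncentral t with 25 cluster-level degrees of freedom: d = 0.49 to 0.53.
- 216 facilitators (the two facilitators of Section 14, both scored in every group; 8 per cluster): d = 0.34 to 0.39 and power 50 to 60%.
- One-sided 0.10, 108 facilitators, no clustering: (1.282 + 0.842) × 2 / √108 = 0.41.
- Repeated assessments per facilitator (k assessments with correlation r, both assumed; ICC 0.05): DE = 1 + (k − 1)r + 3k × 0.05 on 108k scores. This gives 0.38 for k = 4, r = 0.3, and 0.48 for k = 2, r = 0.7.

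None of these reaches 0.26.

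**The case against.** The best reply is that Section 13 gives an overall planning figure for a nonrandomised component study. That study uses a relaxed type I error for component selection and does not bear on the primary effectiveness outcomes. The facilitator ICC is also unknown, and Section 15 does not say that each facilitator is assessed only once. All of this is fair. It limits the importance of the point and makes the exact facilitator figure conditional, but it does not make an adult count applicable to a facilitator score.

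Four stronger readings are tempting, and the documents do not support them.

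- **Fidelity is underpowered too.** It is reported by facilitators, so the adult-based 0.26 was not derived for it. But reports are made per session, and the detectable effect depends on a within-facilitator correlation that the protocol does not give. Plausible values include 0.26, so no direction can be claimed.
- **The participation figure is wrong and should be 0.28.** That picks one reading of an unlabelled 480. With 1,080 adults in 27 clusters of 40, 0.26 is reproduced. Only the label and the cluster size are unclear.
- **The low power is what makes a null result unsafe as proof of no difference under Hypothesis 5A.** A non-significant result would not establish no difference at 80% power either. Low power aggravates that problem but does not create it.
- **One facilitator per group in Section 8 against two in Section 14 explains the gap.** That is a separate inconsistency, and Step 3 shows that doubling the count would not restore 0.26.

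**Conclusion.** The point holds for competent adherence. As written, Section 13 attaches d = 0.26 to an outcome whose detectable effect is about 0.48 to 0.51 with 108 facilitators, or 0.51 to 0.54 with 96. The power at 0.26 is 35 to 39%, or 32 to 36%, against the stated 80%. These figures rest on a two-sided 0.10 test, equal levels, one score per facilitator and an ICC between 0 and 0.05. A higher ICC widens the gap. Repeated scoring or twice the facilitators narrows it without closing it.

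For fidelity, the conclusion is only that 0.26 has no derivation. For participation, it is only that the figure cannot be checked until the 480 is explained. The primary effectiveness analysis is not affected. This should be corrected, but it does not threaten the trial.

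**What to change.** In Section 13:

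1. Remove competent adherence from the outcomes covered by d = 0.26. State a facilitator-level detectable effect of about 0.5, with the facilitator count (108, or 96 after cluster loss), the assumed ICC and a range, for example 0.48 to 0.66 for 108 facilitators with ICC from 0 to 0.30.
2. Do not present the adult-based 0.26 as derived for facilitator-reported fidelity.
3. Say whether the 480 adults are a total or a count per component level, and give the cluster size used, so that the participation figure can be checked.

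This is a change of wording. It needs no extra enrolment and no change of design. The cost is that the stated sensitivity for competent adherence becomes less favourable.

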Parents allocated to the control arm will receive a two-hour structured lecture called *Parenting in a Nutshell* on parenting and partner relationships. Three topics will be covered: 1) child development; 2) positive parenting; and 3) resolving partner conflicts. Facilitators delivering this lecture will have same/similar expertise with the facilitators engaged in PfR. Their training will consist of two-hour course on how to deliver the lecture.

15. Outcomes measurements

All outcomes of intervention effectiveness will be measured at baseline, 8-months post-baseline, and 12-months post-baseline. Demographic measures will only be measured at baseline. All measures will be translated into Luganda for Wakiso and Acholi for Amuru and back-translated to check the accuracy of the translation.

Primary outcomes

Child maltreatment - physical and emotional abuse: ISPCAN Child Abuse Screening Tool-Trial Parent (ICAST-TP) - Parent Report

Child maltreatment will be measured using an adapted version of the ISPCAN Child Abuse Screening Tool-Trial scale (17 items, ICAST-Trial) [26]. The original version of the ICAST-Trial was reduced from 19 items for caregivers and 27 items for adolescents to increase study feasibility due to the scale of the study. Respondents will report on the overall frequency of maltreatment during the past month as

well as for subscales on physical abuse (10 items; e.g., “In the past 4 weeks, how often did you discipline your child by spanking, slapping or hitting with your hand”) and emotional abuse (7 items; e.g., “In the past 4 weeks, how often did you say things to shame your child in front of other people?”). Each item ranges from 0 to more than 8 times and is summed to assess frequency of overall abuse as well as for each individual subscale.

[Time Frame: Baseline, 8-months post-baseline, and 12-months post-baseline]

Child maltreatment - physical and emotional abuse: ISPCAN Child Abuse Screening Tool-Trial Parent (ICAST-TC) - Child Report on Male Parent Figure

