Educational re-enrolment will be assessed for children who are not currently in school by asking parents whether or not they would want them to go back to school (0=No, 1=Yes).

[Time Frame: Baseline, 8-months post-baseline, and 12-months post-baseline]

Educational re-enrolment – Child Report

Educational re-enrolment will be assessed for children who are not currently in school by asking children whether or not they would want to go back to school (0=No, 1=Yes).

[Time Frame: Baseline, 8-months post-baseline, and 12-months post-baseline]

Parent support of education – Parent Report

Parental support for school will be measured by asking how often the parent engages in behaviours that support learning using a 5-point Likert scale (5 items, e.g., “I let my child’s schoolwork come first, before chores and responsibilities”). Higher scores reflect more parental support and value for school.

[Time Frame: Baseline, 8-months post-baseline, and 12-months post-baseline]

Parent support of education – Child Report

Parental support for school will be measured by asking how often the child’s male and female parent figures engage in behaviours that support learning using a 5-point Likert scale (10 items, e.g., “Your

male/female parent figure lets your schoolwork come first, before chores and responsibilities”). Higher scores reflect more parental support and value for school.

[Time Frame: Baseline, 8-months post-baseline, and 12-months post-baseline]

Child behaviour problems: Child and Adolescent Behaviour Inventory – Adult Report

Child behaviour problems will be measured using the Child and Adolescent Behaviour Inventory (CABI) [31]. The CABI assesses a wide range of internalising and externalising symptoms in children and adolescents and is relatively shorter than the Child Behaviour Check List (CBCL), making it a practical and reliable tool for measuring behaviour problems. Parents report on their child’s behaviour during the past month (0 = Not True, 1 = Somewhat or Sometimes True, 1 = Very True). The irritability subscale (4 items, e.g., “has frequent mood changes”) and the externalizing subscale (10 items, e.g., often lies or cheats) will be used to measure problem behaviours. The 14 items are summed to create a total score of child behaviour problems.

[Time Frame: Baseline, 8-months post-baseline, and 12-months post-baseline]

Child behaviour problems: Child and Adolescent Behaviour Inventory – Child Report

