Relative poverty will be assessed using an adapted version of the *Basic Necessities Scale* (6 items). Developed by the Centre for South African Social Policy in the ‘Indicators of Poverty and Social Exclusion Project,’ the Basic Necessities Scale measures levels of economic deprivation by identifying basic household items that families are unable to afford [37]. These include food, toiletries, clothes, shoes, and school uniforms, equipment, and fees. Items are coded dichotomously for positive or negative responses and summed to create an overall score.

[Time Frame: Baseline]

Family stressors – Parent Report

Family stressors will be based on six items measuring the presence or absence of the following challenging situations in each household: adult illness, recent death or illness of a family member, substance use, child illness, child hunger, and child disabilities. Items will be summed to create total score of family-level stressful experiences

[Time Frame: Baseline]

Food insecurity – Adult Report

Food insecurity will be assessed by asking adult respondents to report on whether their household was able to provide meals at breakfast, lunch, and dinner in the past month based on a Likert scale (0 =No; 1=Yes, sometimes; 2=Yes, always).

[Time Frame: Baseline]

Food insecurity – Child Report

Food insecurity will be assessed by asking child respondents to report on whether their household was able to provide meals at breakfast, lunch, and dinner in the past month based on a Likert scale (0 =No; 1=Yes, sometimes; 2=Yes, always).

[Time Frame: Baseline]

Basic caregiver and child demographic information – Child and Adult Report

Basic caregiver and child demographic information will be asked using items from the UNICEF Multiple Indicators Cluster Survey (MICS) Household Survey [29]. The MICS was developed to monitor the situation of children and women on a global level and is based on Demographic and Health Surveys. It has been used widely throughout low- and middle-income countries (LMIC) including Uganda. In our study, we will collect data on caregiver/child age, caregiver/child gender, caregiver religion, caregiver educational status, caregiver/child literacy and disability, number of adults and children living in the household, child's relationship to caregiver, presence of child's biological parents and other caregivers in the household, child enrolment in school, and marital status.

[Time Frame: Baseline]

Process outcomes

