The intervention arm (PfR) will be compared against the control (lecture) for all primary and secondary outcome analyses. All analyses will be conducted with an intention-to-treat design using full expectation maximum likelihood (FEML). Baseline differences between intervention and control groups will be examined for demographic data and outcome measures using independent t-tests and Chi-square crosstab analyses. Treatment effects will be estimated for post-treatment outcomes using two-tailed Poisson regression mixed-level models for skewed outcomes and multi-level regression analyses for continuous variables, adjusting for clusters and controlling for baseline outcome levels. In order to assess the potential clinical relevance of outcomes in this pilot study, we will examine tests for significance of effect (set at the $p < 0.05$ level), as well as the direction and magnitude of incidence risk ratios (IRRs) [46]. While tests for significance based on p -values may determine whether there is a statistically reasonable likelihood of detecting an intervention effect, the estimation of effect sizes is generally recommended as a more appropriate approach for studies with small sample sizes [47].

Testing theory of change

Intervention research provides an opportunity to test theoretical mechanisms and causal processes related to the role of parenting programmes in reducing risk of child maltreatment [48]. As aforementioned, this study tests two hypothesized pathways of change. Firstly, improved parenting knowledge, skill and sense of competence will increase positive parenting and reduce maltreatment. Secondly, improving caregiver mental health, intimate partner violence, and child behaviour will also mediate reductions in risk of child maltreatment. Multiple linear regression analyses [49] and structural equation modelling [50] will examine these hypotheses based on the aforementioned proximal and secondary outcomes. In addition, qualitative focus groups will provide further information regarding the mechanisms involved and essential programme elements necessary for effectiveness in other settings [51].

Testing interaction effects

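### The two secondary outcomes named educational re-enrolment record a wish, not a return, and a child who goes back to school leaves the denominator

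*Protocol*

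**What the plan says.** Section 15 of the protocol (Outcomes measurements, Secondary outcomes) lists educational re-enrolment twice.

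- Version for parents: "Educational re-enrolment will be assessed for children who are not currently in school by asking parents whether or not they would want them" (the wish is for a return to school), coded 0 = no, 1 = yes.
- Child report: the same restriction to children out of school, assessed "by asking children whether or not they would want to go back to school", with the same coding.
- Both carry the schedule "Time Frame: Baseline, 8-months post-baseline, and 12-months post-baseline".

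Actual enrolment appears elsewhere in Section 15, in the basic demographic information, whose list ends "child enrolment in school, and marital status" and whose time frame is baseline. The opening of Section 15 confirms this: "Demographic measures will only be measured at baseline". No outcome in the protocol is defined as return to school, and nothing says how a child who has returned is to be scored on the two items.

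Section 20 (Intervention effectiveness) applies intention to treat to all analyses and adjusts for the baseline level of the outcome.

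**The concern.** The name promises a behaviour, but the item records an attitude. Educational aspirations and expectations are already separate outcomes in Section 15, so a reader of the results would naturally take re-enrolment to mean that the child went back to school.

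The more statistical problem is who is asked. At 8 and 12 months the word *currently* ties the item to status at that visit, which is after randomisation and may be affected by the programme. A child who returns, which is the event the outcome is named for, drops out of numerator and denominator alike. A child who leaves school after baseline enters the denominator with no baseline value for the planned adjustment. The two arms are then compared on sets of children that the intervention may itself have shaped, which sits badly with the intention-to-treat statement in Section 20.

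At stake is the reading of two secondary outcomes. A real gain in school return would not be counted, and under some conditions it would show as a lower proportion in the arm that achieved it.

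**Working it through.** The protocol gives no out-of-school share, wish rate, expected effect or power for these outcomes, so there is no figure to reproduce. The only documented input is about 540 children per arm (Section 8). Everything else below is an assumption, used to show the direction and possible size.

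**Set-up.** Among children out of school at baseline, let *w* be the share with a yes on the wish item. Let *r₁* be the fraction of these wishers back in school by the visit, and *r₀* the fraction of non-wishers back. Assume that no answer changes and that nobody newly leaves school. The proportion of yes answers at follow-up, as the outcome is written, is

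w(1 − r₁) / [w(1 − r₁) + (1 − w)(1 − r₀)].

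- If r₁ = r₀, this equals *w*, so return unrelated to the wish does not move the proportion.
- If r₁ > r₀, it falls below *w*.
- If r₀ = 0 (only wishers return), it becomes (w − w·r₁) / (1 − w·r₁).

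**One worked case.** Assume 10% of 540 out of school, which is 54 per arm, *w* = 0.80, no returns in control, half of the wishers returning in the intervention arm, and r₀ = 0.

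- As written, control: 43.2 / 54 = 80.0%.
- As written, intervention: (43.2 − 21.6) / (54 − 21.6) = 21.6 / 32.4 = 66.7%. The arm that returned children looks 13.3 points worse.
- Actual return on the fixed baseline denominator: 0 / 54 = 0% against 21.6 / 54 = 40%, in favour of the intervention.

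**Range.** With r₀ = 0 and no control returns:

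| *w* | *r₁* | As written, control | As written, intervention | Apparent loss (points) | Actual return, intervention |
|---|---|---|---|---|---|
| 0.60 | 0.25 | 60.0% | 52.9% | 7.1 | 15% |
| 0.60 | 0.75 | 60.0% | 27.3% | 32.7 | 45% |
| 0.80 | 0.25 | 80.0% | 75.0% | 5.0 | 20% |
| 0.80 | 0.75 | 80.0% | 50.0% | 30.0 | 60% |
| 0.95 | 0.25 | 95.0% | 93.4% | 1.6 | 24% |
| 0.95 | 0.75 | 95.0% | 82.6% | 12.4 | 71% |

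The extremes check as 0.15 / 0.55 = 27.3% and 0.7125 / 0.7625 = 93.4%. The out-of-school share changes the counts (27 to 162 per arm for 5% to 30%) but not these proportions.

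**Softer assumptions.** The loss shrinks when they are relaxed.

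- If 10% of control wishers and 50% of intervention wishers return, the difference is 14.6, 11.6 or 4.0 points for *w* = 0.60, 0.80 or 0.95. For *w* = 0.80: 0.72 / 0.92 = 78.3% against 0.40 / 0.60 = 66.7%.
- If a quarter of non-wishers also return in the intervention arm (*w* = 0.80, r₁ = 0.50, r₀ = 0.25, no control returns), the proportion is 0.40 / (0.40 + 0.20 × 0.75) = 0.40 / 0.55 = 72.7%, a loss of 7.3 points.

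**The case against.** A reader might infer three stronger things, none of which the protocol supports.

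*That the comparison is necessarily biased against the better arm.* It is not. The shift needs wishers to return more often than non-wishers, which is plausible but nowhere stated. Families unable to send a child back may still answer yes, and that does not lower the proportion. With a near-universal wish the shift can be under 2 points.

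*That school status at follow-up will be unknown.* The filter at 8 and 12 months can be applied only if someone establishes whether the child is in school. Baseline enrolment together with that answer would identify the returners. The protocol does not, however, schedule the answer as a recorded item or define an outcome from it.

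*That a benefit under Hypothesis 3 would be lost or reported as harm.* Hypothesis 3 names parental support for education, which has its own multi-item scales in Section 15 (5 parent items, 10 child items). Actual return to school is not named in the objectives or hypotheses. A significant reversal is also unlikely outside extreme cases. In the worked case of 54 per arm the standard error is √(0.8 × 0.2 / 54 + 0.667 × 0.333 / 32.4) ≈ 0.099, so z ≈ 0.133 / 0.099 ≈ 1.35 before any allowance for clustering.

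It can also be argued that this is an attitude item with a poor label, and that scoring belongs in a statistical analysis plan. The label point is fair and is part of the fix. The second argument stands only in part: who is asked, what is asked and at which visits are set in the protocol, and an analysis plan cannot use a status that was not kept.

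**Conclusion.** The point holds in a limited form. As written, both outcomes measure a wish among children out of school at each visit. No actual return is counted, and the follow-up denominator is defined after randomisation. That much follows from the text and needs no assumption.

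Bias against the arm that returns more children is possible, not certain, and depends on wishers being likelier to return. Its size cannot be determined from the protocol. Over the assumed ranges (wish rate 60–95%, 25–75% of wishers returning in one arm only, no non-wishers returning) the apparent loss is about 2 to 33 points. It is smaller if controls or non-wishers also return, and zero if return is unrelated to the wish.

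The consequence is confined to two secondary outcomes in what may be a small subgroup. It is worth correcting before follow-up, because a status not recorded at 8 and 12 months may not be recoverable.

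**What to change.** 1. Record the existing school-enrolment item explicitly at 8 and 12 months, and exempt it from the baseline-only rule for demographic measures.
2. Define re-enrolment as enrolled at the follow-up visit among children out of school at baseline. That denominator is fixed before randomisation and agrees with the intention-to-treat statement.
3. Keep the question on wanting to go back as a descriptive attitude measure under a different name, reported for those to whom it applies.

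The cost is one yes/no question, which the filter already implies, at two visits, plus a reworded definition. Section 27 requires a formal amendment for changes to data collection and analysis. The downside is precision: the group out of school at baseline may be small (27 per arm if the share were 5%, an assumed figure), so the estimate should be presented as imprecise.
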